## SECTION I: RESEARCH PLAN

1. **Statement of Purpose:** State the scientific aim(s) of the study, or the hypotheses to be tested.

The proposed project will use wearable technology to test the feasibility and efficacy of delivering a novel real-time smoking intervention to improve standard tobacco treatment. 50 adult daily smokers will be recruited from an outpatient tobacco treatment center to participate in an 8-week pilot intervention. Participants will be randomly assigned to a control group (standard treatment ST, n=25) or experimental group (standard treatment plus real-time smoking intervention ST+, n=25). The control group (ST) will not receive real-time feedback about their smoking. The experimental group (ST+) will receive real-time feedback as soon as smoking is detected using wearable technology during the 8-week intervention. Specific aims include:

**Aim 1: Evaluate the feasibility, acceptability, and helpfulness of the real-time smoking intervention.** We will characterize rates of adherence (i.e., number of days wearing the smartband) and evaluate participant satisfaction and perceived usefulness of the intervention using post-treatment interviews and ratings.

**Aim 2: Assess the preliminary efficacy of the real-time intervention as an adjunct to standard tobacco treatment.** We will compare biochemically confirmed 7-day point prevalence abstinence at the end of treatment (week 8) to estimate effect sizes for ST+ vs. ST. Additional outcomes will compare total number of days abstinent and changes in cigarettes per smoking day from baseline to end of treatment between ST+ and ST as proximal indices of good clinical response that are related to long-term cessation outcomes.

2. **Probable Duration of Project:** State the expected duration of the project, including all follow-up and data analysis activities.

2 years. We anticipate recruiting and enrolling 50 subjects over 20 months and will complete data entry and analysis by the end of 2 years.

3. **Background:** Describe the background information that led to the plan for this project. Provide references to support the expectation of obtaining useful scientific data.

[figure not shown]

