**Overview:** The proposed study will evaluate the feasibility and efficacy of a real-time smoking intervention as an adjunct to enhance standard tobacco treatment. 50 adult smokers will be randomly assigned to a control group (standard tobacco treatment, ST, n=25) vs. an experimental group (standard treatment plus a real-time smoking intervention, ST+, n=25). Randomization to group (1:1) will be stratified by average number of cigarettes smoked per day at baseline (< or ≥ 10 cigarettes per day) to balance groups on smoking intensity. Enrolled participants will complete research visits at 4 weeks and 8 weeks (see Figure 1). Participants will receive financial compensation for their time spent completing research activities: \$20 for each appointment (week 0,4,8) for a total of \$60. Participants will earn a \$20 bonus for attending the last visit (week 8) and returning the smartband and charger. These visits will take place remotely in which the participant will speak with our research staff by phone or video call, at the tobacco clinic, at our research office, or at a location that is convenient, such as a public place.

**Recruitment:** We will recruit from the Yale Tobacco Treatment Service (TTS) and the Winchester chest clinic. These programs are a specialized outpatient services at Yale-New Haven Hospital that provides individual tobacco treatment to a large patient

population of current smokers. New patients referred to the TTS and Winchester chest clinic will be informed about the study and will be invited to set up a screening appointment if interested. To facilitate participant enrollment and retention, study procedures may take place in person or remotely (e.g., phone, secure video conference) when possible.

Screening Assessments: To screen for eligibility, participants will complete the following assessments including: 1) Smoking history to assess smoking quantity and frequency such as number of cigarettes per day and number of years smoked, 2) self-reported other tobacco and drug use for the past 30 days. Participants may also complete biochemical verification of smoking status, such as breath carbon monoxide (CO) measured in parts per million or cotinine measured in a small sample of urine or saliva.

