Experimental Methods: Eligible participants will be randomized to one of two treatment conditions (ST vs. ST+). All participants will receive standard outpatient tobacco treatment (ST) at the Yale Tobacco Treatment Service (TTS) or Winchester chest clinic following clinical practice guidelines. All patients receive up to 8 sessions of one-on-one counseling which focuses on setting a quit date within the first 2 weeks of treatment and discusses coping strategies and relapse prevention. Patients are encouraged to try smoking cessation pharmacotherapy and can obtain these medications over the counter or by prescription from the TTS or Winchester chest clinic. The experimental group (ST+) will receive standard care plus an adjunct treatment which involves wearing a smartband for the 8-week study and receiving real-time notifications as soon as smoking is detected with the embedded geospatial movement sensors in the smartband. There are multiple commercially available smartbands/smartwatches that are compatible with the real- time smoking monitoring system; for example, the Asus Zenwatch 2 pairs with the user's smartphone via Bluetooth connection. When smoking is detected, an alert is sent to the user through the band (vibration) and their smartphone app (alert) with a message indicating that smoking was just detected. The user can indicate yes/no if this smoking detection was accurate. Real-time smoking data is recorded for the user to review in their smartphone app and is available for the research team to view on a password-protected secure online dashboard. Data include only the timing and number of smoking events, labeled by subject ID. This real-time notification may disrupt the automaticity of smoking behavior and help bring awareness to smoking and related cues in the moment, which may enhance the individual's ability to anticipate and respond adaptively to cues in the future. The control group will also receive the smartband to wear for the 8 week study to control for demands associated with remembering to wear the band and charge it.

Measures: Baseline measures will be used to characterize the sample. Repeated measures will be used to assess changes in smoking and related constructs during treatment.

Demographic Questionnaires (week 0): Age, gender, marital status, employment status, occupation.

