Smoking History (week 0): Smoking characteristics will be assessed, including the number of years of cigarette use, length of prior quit attempts, and prior treatments used.

Quitting Motivation and Confidence (week 0): Readiness to quit smoking and confidence quitting smoking will be measured on an 11-point scale (0=not at all, 10=extremely) using the contemplation ladder.

Discounting task (week 0): A brief computerized discounting task will be administered (5 questions each) to assess choice preference for cigarettes and money. Participants choose between a hypothetical smaller sooner reward or larger later reward, which is a validated measure of decision-making that has been shown to relate to treatment outcomes.

Timeline Follow-Back Interview (TLFB) (week 0,4,8): A standardized, validated, and reliable interview will be used to obtain quantity and frequency estimates of tobacco use, alcohol, and other drugs for the 30-days prior to baseline and at each research visit.

Biochemical Verification of Smoking Status (week 0,4,8): Assessed when needed to confirm reported abstinence via either expired breath carbon monoxide (CO) levels, which have a half-life of 2 hours or cotinine measured in a small sample of urine or saliva.

Nicotine Dependence (week 0,8): Measured by the Fagerström Test for Nicotine Dependence and the 4-item NIH PROMIS® measure for daily smokers.

Craving (week 0,4,8): Measured by the Questionnaire of Smoking Urges-Brief (QSU-Brief).

Strength of Smoking Habit (week 0,4,8): Measured with a 6-item Self-Report Habit index adapted and validated for smoking behavior, e.g. “Smoking is something I do automatically” rated on a 5-point scale (1=strongly disagree, 5=strongly agree).

Perceived Control Over Smoking (week 0,4,8): Measured with 3 valid, reliable items rated on a 7-point scale that have demonstrated associations with smoking outcome, e.g., “How much control do you feel you have over not smoking?” (1=no control, 7=complete control).

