Approach-Avoidance Task (AAT) (week 0, 4, 8): An objective behavioral task that measures the tendency to automatically approach smoking stimuli (e.g., cigarettes). Our research team has used an adapted version of the approach-avoidance task (AAT) to measure smoking approach and avoidance action tendencies. The task starts with 20 practice trials in which participants learn to push or pull the joystick in response to picture format (landscape or portrait). The practice phase is followed by 160 test trials in which pictures of cigarette stimuli (e.g., cigarettes, cigarette packages) and non-cigarette stimuli (e.g., pencil) come equally in

push- or pull-format (this takes 5 to 10 minutes). Picture format (landscape or portrait) to response assignment (push or pull) is counterbalanced, with half the participants pulling landscape pictures and half portrait pictures. The smoking approach bias represents the relative difference between pushing and pulling the joystick in response to the smoking stimuli, measured as mean reaction time. Evidence supports reliable approach tendencies related to substance use and indicates that meaningful changes in automatic approach tendencies related to substance use outcomes can be detected after one week.

End of Treatment Ratings (week 8): We will evaluate participant satisfaction and perceived usefulness of the treatment across both conditions with post-treatment interviews and ratings.

Analytical Plan:

Data Management and Statistical Analyses: The proposed study will follow HIPAA guidelines for data collection, management, and monitoring. Data analyses will use the intention-to-treat (ITT) principle, where missing data will be treated as smoking. Data analyses will be conducted under the supervision of [name] who is a biostatistician. Data on quantitative outcomes will be examined for conformity to the normal distribution and transformation or non-parametric methods will be used if necessary.

Aim 1: Evaluate the feasibility, acceptability, and helpfulness of the real-time smoking intervention. We will use descriptive statistics to summarize participant ratings of satisfaction and perceived usefulness of the intervention at the end of treatment, including characterizing adherence and feasibility of using the smartband device based on self-report and objective adherence (i.e., number of days wearing the smartband).

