Aim 2: Assess the preliminary efficacy of the real-time intervention as an adjunct to standard tobacco treatment. We will compare biochemically confirmed 7-day point prevalence abstinence at the end of treatment (i.e., reported abstinence from cigarettes during the last week of the study that is confirmed with CO≤ 4ppm or cotinine measured in a small sample of urine or saliva) to estimate effect sizes for ST+ vs. ST. We will also compare continuous outcome measures between ST+ and ST that are proximal indices of good clinical response: number of days abstinent and changes in cigarettes per smoking day from baseline to week 8. We will use independent sample t-tests to compare total days abstinent between ST+ and ST and a 2x2 mixed ANOVA (time x condition) to compare changes in cigarettes per smoking day from baseline to week 8.

5. Genetic Testing    N/A

A. Describe

- i. the types of future research to be conducted using the materials, specifying if immortalization of cell lines, whole exome or genome sequencing, genome wide association studies, or animal studies are planned *Write here*
- ii. the plan for the collection of material or the conditions under which material will be received *Write here*
- iii. the types of information about the donor/individual contributors that will be entered into a database *Write here*

HIC# 2000024740

iv. the methods to uphold confidentiality *Write here*

- B.** What are the conditions or procedures for sharing of materials and/or distributing for future research projects? *Write here*
- C.** Is widespread sharing of materials planned? *Write here*
- D.** When and under what conditions will materials be stripped of all identifiers? *Write here*
- E.** Can donor-subjects withdraw their materials at any time, and/or withdraw the identifiers that connect them to their materials? *Write here*
  - i. How will requests to withdraw materials be handled (e.g., material no longer identified: that is, anonymized) or material destroyed)? *Write here*
- F.** Describe the provisions for protection of participant privacy *Write here*
- G.** Describe the methods for the security of storage and sharing of materials *Write here*

6. **Subject Population:** Provide a detailed description of the types of human subjects who will be recruited into this study.

*Write here*

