**Inclusion Criteria:**

- (a) age 18 or older
- (b) daily cigarette smoker
- (c) seeking smoking cessation treatment at Yale TTS or Winchester chest clinic
- (d) able to read and write in English
- (d) owning a smartphone

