**Data Quality and Management:**

[name] will supervise and train the Research Assistant and all key personnel on study procedures to ensure that all procedures are followed and are in compliance with the approved Yale University IRB protocol. [name] will also provide training and oversight to study staff to ensure data are generated, documented, and reported according to requirements by the Yale University IRB and the funding source. The Biostatistician, [name], will also oversee quality assurance of data.

d. For multi-site studies for which the Yale PI serves as the lead investigator:

- i. How will adverse events and unanticipated problems involving risks to subjects or others be reported, reviewed and managed? *Write here*
- ii. What provisions are in place for management of interim results? *Write here*
- iii. What will the multi-site process be for protocol modifications? *Write here*

12. **Statistical Considerations:** Describe the statistical analyses that support the study design.

*Write here*

**Aim 1: Evaluate the feasibility, acceptability, and helpfulness of the real-time smoking intervention.** We will use descriptive statistics to summarize participant ratings of satisfaction and perceived usefulness of the intervention at the end of treatment, including characterizing adherence and feasibility of using the smartband device based on self-report and objective adherence (i.e., number of days wearing the smartband).

**Aim 2: Assess the preliminary efficacy of the real-time intervention as an adjunct to standard tobacco treatment.** We will compare biochemically confirmed 7-day point prevalence abstinence at the end of treatment (i.e., reported abstinence from cigarettes during the last week of the study that is confirmed with  $CO \leq 4 \text{ ppm}$ ) to estimate effect sizes for ST+ vs. ST. We will also compare continuous outcome measures between ST+ and ST that are proximal indices of good clinical response: number of days abstinent and changes in cigarettes per smoking day from baseline to week 8. We will use independent sample t-tests to compare total days abstinent between ST+ and ST and a 2x2 mixed ANOVA (time x condition) to compare changes in cigarettes per smoking day from baseline to week 8.

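### Change in cigarettes per smoking day is undefined for anyone with no smoking day in the unstated week-8 window and has no count for dropouts, so the planned ANOVA needs a rule the plan does not give

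*Combined protocol and SAP*

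**What the plan says.** Section I, item 1 (Aim 2) lists "changes in cigarettes per smoking day from baseline to end of treatment between ST+ and ST as proximal indices of good clinical response" as one of two additional outcomes; the other is days abstinent. The Analytical Plan in Section I, item 4 tests it with "a 2x2 mixed ANOVA (time x condition) to compare changes in cigarettes per smoking day from baseline to week 8". Section I, item 12 repeats the outcome ("changes in cigarettes per smoking day from baseline to week 8") and the test.

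The general analysis rule, under Data Management and Statistical Analyses in item 4, is intention to treat, "where missing data will be treated as smoking". The only other provision for quantitative outcomes there is a transformation or a non-parametric method if the distribution is not normal.

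The data come from the Timeline Follow-Back interview (TLFB) at weeks 0, 4 and 8, taken "for the 30-days prior to baseline and at each research visit". All participants enter as a "daily cigarette smoker" (item 8), and counselling aims at "setting a quit date within the first 2 weeks of treatment" (item 4, Experimental Methods).

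The sample size section in item 12 gives a detectable difference of 6 cigarettes per smoking day (SD 8) at 80% power and two-sided 5% alpha, with 25 per group.

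The documents do not give a week-8 window for this outcome, a value for a participant with no smoking day, a cigarette count for a dropout, or an analysis set for the test.

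**The concern.** The measure is total cigarettes divided by number of smoking days. A participant who quit and stayed quit through the window has zero over zero. Such a person has attended and is not missing, so the missing-data rule does not reach them. A dropout is reached by the rule but receives only a status. That settles the yes/no abstinence outcome and leaves this one without a number. A transformation or a rank method cannot act on a value that does not exist.

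The 2x2 mixed ANOVA needs both time points for each person. If nothing is added, the participants who enter it are those who attend week 8 and still smoke. Membership of that group depends on the behaviour that the intervention is meant to change, and it is expected to shrink more in the arm with more quitters. The best responders would then have no score on an outcome chosen as an index of good response, and the comparison would depart from the stated intention-to-treat principle. If a rule is chosen only after the data are seen, the estimate depends on that choice.

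**Working it through.** **Inputs from item 12.** 25 per group; difference 6, SD 8 (standardised 6/8 = 0.75); two-sided alpha 0.05; power 0.80; abstinence rates in ST+ and ST of 25/15%, 30/15% and 35/20%. The documents give no dropout rate and no rate of biochemical confirmation, so those below are assumptions.

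**The plan's own figure.** The time-by-condition interaction in a 2x2 mixed ANOVA is equivalent to a two-sample t-test on change scores. With 25 per group, SE = 8 × √(1/25 + 1/25) = 2.26. Noncentral-t power for 6 cigarettes is 73.8%, and the difference detectable with 80% power is 6.47. The normal approximation gives 75.5% and 6.34. The stated 6 is therefore somewhat optimistic before anyone is lost. That is a separate issue; 73.8% serves here only as the starting point.

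**Loss of participants without a value.** Evaluable n per arm = 25 × (1 − k × p), where p is the planned abstinence rate and k scales it. If k = 0.5, half of the confirmed abstainers lack a value; if k = 1, all do. If k = 1.25, only 80% of self-reported abstainers are confirmed (assumed), so 1/0.8 times as many report no smoking day. No dropout.

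| k | Rates (%) | n ST+ / ST | Lost of 50 | Power | 80%-power difference |
|---|---|---|---|---|---|
| 0.5 | 25/15 | 21.9 / 23.1 | 5.0 | 69.1% | 6.84 |
| 0.5 | 30/15 | 21.25 / 23.1 | 5.6 | 68.4% | 6.89 |
| 0.5 | 35/20 | 20.6 / 22.5 | 6.9 | 67.1% | 7.00 |
| 1 | 25/15 | 18.75 / 21.25 | 10.0 | 63.6% | 7.29 |
| 1 | 30/15 | 17.5 / 21.25 | 11.25 | 61.9% | 7.43 |
| 1 | 35/20 | 16.25 / 20.0 | 13.75 | 58.8% | 7.70 |
| 1.25 | 25/15 | 17.2 / 20.3 | 12.5 | 60.5% | 7.55 |
| 1.25 | 30/15 | 15.6 / 20.3 | 14.1 | 58.1% | 7.76 |
| 1.25 | 35/20 | 14.1 / 18.75 | 17.2 | 54.0% | 8.16 |

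**Whole-treatment window.** Every attendee smoked daily at entry, so nearly all would have a smoking day, and the remaining loss is dropout. At an assumed 10%, 20% or 30% in each arm (22.5, 20 or 17.5 per arm), power is 69.1%, 63.7% or 57.7%. A participant who quits by day 14 and stays quit would be scored on at most about 14 of 56 days, all before quitting.

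**Effect of the rule on the estimate.** Suppose continuing smokers smoke m per smoking day at week 8 in both arms, change equally, and baseline is unrelated to quitting. Leaving quitters out gives a between-arm difference of 0. Scoring them 0 gives (p1 − p0) × m in favour of ST+. With an assumed m = 10 this is 0.10 × 10 = 1.0 or 0.15 × 10 = 1.5 cigarettes; for m from 5 to 15 the range is 0.5 to 2.25.

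**Selection among those left.** If quitting is tied to the change score through a latent normal variable with correlation ρ, the shift is 8 × ρ × [φ(z_p1)/(1 − p1) − φ(z_p0)/(1 − p0)]. At an assumed ρ = 0.5 this is 0.60, 0.89 and 0.88 cigarettes for the three rate pairs. Against SEs of 2.53, 2.58 and 2.67 (k = 1), that is 0.24, 0.34 and 0.33 SE. The sign follows ρ.

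**The case against.** The plan never adopts a complete-case analysis. It commits to intention to treat, and a sensible analyst could supply a rule that keeps everyone in. This stands. A reader might infer that the test as planned cannot compare the groups as randomised; the documents support only that it will not do so unless a rule is added.

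The loss of quitters also depends on the window. The TLFB wording can be read in more than one way, and interviews at weeks 0, 4 and 8 might support a whole-treatment average. That reading sits less easily with a baseline-to-week-8 time factor but is not excluded, and it would nearly remove the loss among attendees. It would not give dropouts a count, and the plan does not state it.

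A reader might also take 10 to 14 lost as a worst case. It is not a bound. The planning rates are for confirmed abstinence with missing counted as smoking, so unconfirmed self-reported abstainers would add to the loss, while a longer window would reduce it.

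The selection shift is small against the standard error and its direction is unknown, so no definite bias can be claimed. Finally, replacing the outcome and the model goes further than closing the gap requires. The ANCOVA in particular does nothing about undefined values. That is fair, and a minimum alternative is given under the fix.

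**Conclusion.** The concern holds as a gap in the definition of a tested outcome. No rule covers participants with no smoking day or dropouts. With a short week-8 window and nothing added, the test leaves out the successful quitters, contrary to the plan's own analysis principle.

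If the planned abstainers are the ones without a value, with a 7-day window and no dropout, 10 to 14 of 50 are lost and power falls by 10 to 15 points, from 73.8% to 59-64%. If half of them lack a value, it is 67-69%. At an assumed 80% confirmation, 12.5 to 17 are lost and power is 54-61%. These are scenarios, and the defect itself does not depend on them. The shortfall of the starting 73.8% from 80% should not be charged to this point.

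The matter should be fixed, but its reach is limited. Confirmed 7-day abstinence and Aim 1 are untouched, and this is one of two additional continuous outcomes in a 50-person pilot.

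**What to change.** For the between-arm test, use mean cigarettes per calendar day from the TLFB over a fixed week-8 window (for example the last 7 days), counting abstinent days as 0, in all randomised participants. Give dropouts a numeric value consistent with missing counted as smoking, for example baseline cigarettes per day. Analyse by ANCOVA with baseline cigarettes per day as covariate; it is already collected, and its split at 10 is the stratification factor. Keep cigarettes per smoking day as a description of continuing smokers, with n by arm, and restate the detectable difference for the outcome actually tested.

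If cigarettes per smoking day remains the tested outcome, the minimum is to fix four things in advance: the window, the value for zero smoking days, the count for dropouts and the analysis set.

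The cost is wording only, since the TLFB already yields the data. Because everyone smokes daily at entry, the baseline value is essentially the same on both measures. There are downsides. The calendar-day mean mixes quitting with reduction and overlaps with days abstinent. Its SD must be assumed afresh, so no gain in power is claimed. The cluster of zeros may trigger the plan's non-parametric fallback. Carrying baseline forward is a single imputation.

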**Sample Size Justification & Power Calculation:** This study is a developmental project testing the feasibility and potential efficacy of adding a novel intervention to enhance standard smoking cessation treatment. Sample size for the current study is based on guidelines for Stage 1 treatment development studies that suggest a minimum of 15 participants per experimental arm to obtain a reliable effect size estimate. Our target sample (25 per group) is sufficient to determine preliminary efficacy and estimate effect sizes for the binary cessation outcome, 7-day point prevalence abstinence at the end of treatment. This sample size produces two-sided 95% confidence intervals for the difference in population proportions with a half-width that is equal to 22%-24% when the difference in abstinence rates between groups (ST+ vs. ST) in estimated sample proportions is 10%-15% (e.g., 25% vs. 15%, 30% vs. 15%,

HIC# 2000024740

35% vs. 20%). For the continuous smoking outcomes, based on power=.80 and two-tailed alpha=.05, we can detect a statistically significant difference between groups of 4 days abstinent (SD=5) and a difference of 6 cigarettes per smoking day (SD=8) between baseline and end of treatment by group.

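### Cigarettes per smoking day is tested as a change score although ANCOVA on the baseline already collected would be more precise, and no Aim 2 analysis uses the stratification factor

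*Combined protocol and SAP*

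**What the plan says.** The Aim 2 analyses are set out in Section I, item 4 (Analytical Plan) and repeated in Section I, item 12 (Statistical Considerations).

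- **Cigarettes per smoking day:** "a 2x2 mixed ANOVA (time x condition) to compare changes in cigarettes per smoking day from baseline to week 8".
- **Days abstinent:** "We will use independent sample t-tests to compare total days abstinent between ST+ and ST".
- **7-day point prevalence abstinence:** the arms are to be compared to estimate an effect size; no test or model is named.

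No covariate appears in any of these. The only flexibility is in the Data Management and Statistical Analyses paragraph, where "transformation or non-parametric methods will be used if necessary".

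Two features of the design bear on this. The Overview says randomisation is "stratified by average number of cigarettes smoked per day at baseline (< or ≥ 10 cigarettes per day) to balance groups on smoking intensity". The Timeline Follow-Back interview, given at weeks 0, 4 and 8, provides "quantity and frequency estimates of tobacco use, alcohol, and other drugs for the 30-days prior to baseline and at each research visit". Baseline smoking is therefore both measured and treated by the design as worth balancing.

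The Sample Size Justification, working at 80% power and a two-sided 5% level, claims for the continuous outcomes: "we can detect a statistically significant difference between groups of 4 days abstinent (SD=5) and a difference of 6 cigarettes per smoking day (SD=8". It does not say whether the 8 is the SD at one visit or the SD of the change.

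**The concern.** A change score uses the baseline value with its coefficient fixed at 1. If the regression of the week-8 value on baseline has a slope other than 1, the change score carries noise that ANCOVA would remove. In large samples ANCOVA is at least as efficient whatever the slope.

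A design that balances arms on a prognostic factor, followed by an analysis that ignores the factor, reports a standard error that is too large. The test stays valid but is conservative.

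What is at stake is precision in a trial of 50 whose Aim 2 product is an effect-size estimate. Choosing a covariate after seeing the data would invite selective reporting, so any adjustment should be written down beforehand.

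**Working it through.** **Inputs from the plan.** 25 per arm, two-sided alpha .05, difference 6 with SD 8 for cigarettes per smoking day, difference 4 with SD 5 for days abstinent, stated half-width 22 to 24 points for abstinence.

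**Assumed, because the plan gives none.** Baseline to week-8 correlation rho, the ratio k of week-8 SD to baseline SD, the share of variance R² explained by the stratum, and stratum sizes.

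**1. The plan's own figures.** Two-sample t, 48 df, noncentrality = difference / (SD × √(2/25)).

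- Days abstinent: 4 / (5 × .2828) = 2.83, power .79 (.81 by normal approximation). This agrees with the plan.
- Cigarettes: 6 / (8 × .2828) = 2.65, power .74. The difference detectable at power .80 is 6.47, which rounds to 6, so the shortfall may be only rounding.

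**2. Equivalence.** With two time points, the time x condition F equals the squared two-sample t on the change score. The two were identical when computed on a simulated data set.

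**3. ANCOVA for cigarettes, taking 8 as the SD of change.** Baseline SD s0 = 8 / √(1 + k² − 2·rho·k). Residual SD = k·s0·√(1 − rho²), tested on 47 df. With k = 1 this reduces to 8·√((1 + rho)/2). At rho .5 that is 6.93, noncentrality 6 / (6.93 × .2828) = 3.06, power .85. There is no gain when k·rho = 1.

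| | rho .3 | rho .5 | rho .7 |
|---|---|---|---|
| Planned change-score test | .74 | .74 | .74 |
| ANCOVA, k = 1 | .90 | .85 | .80 |
| ANCOVA, k = 1.25 | .84 | .79 | .75 |
| ANCOVA, k = .75 | .97 | .95 | .94 |

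The 95% half-width is 4.55 as planned (2.011 × 8 × .2828), against 3.67, 3.94 and 4.20 by ANCOVA at k = 1.

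**4. If 8 is instead the SD at one visit (k = 1).** SD of change = 8·√(2(1 − rho)); ANCOVA residual SD = 8·√(1 − rho²). Power goes from .59 to .78 at rho .3, .74 to .85 at rho .5 and .92 to .95 at rho .7.

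**5. Check under the stratified design.** These are simulated trials of 50, randomised within strata cut at 10 cigarettes per day, with k = 1, SD of change 8 and an assumed baseline mean of 15.

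| | rho .3 | rho .5 | rho .7 |
|---|---|---|---|
| Type I error, planned | .033 | .036 | .041 |
| Power, planned | .76 | .73 | .75 |
| Power, ANCOVA | .89 | .84 | .81 |
| Fall in true SD of the estimate | about 11% | about 6% | about 4% |

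ANCOVA's type I error is about .05. Both estimates are unbiased. A stratum term added to the change-score test gives about .83, .80 and .78.

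**6. Participants with no smoking days.** The measure is undefined for them. If 15%, 25% or 35% (abstinence rates from the sample-size section) drop out of this outcome, about 21, 19 or 16 per arm remain (25 × .85, .75, .65). Planned power is then .66, .61 or .54; ANCOVA at rho .5, k = 1 gives .78, .74 or .66.

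**7. Days abstinent.** Simulation with SD 5 and strata of 20 and 30 balanced by arm:

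- At R² = .10 the true SD of the estimate is 1.34 with or without the stratum. The mean reported SE is 1.41 unadjusted and 1.33 adjusted, so it is about 6% too large when the stratum is left out (about 3% at R² = .05).
- Unadjusted type I error is about 4.5% at R² = .05 and 4% at R² = .10.
- Power goes from .80 to .81 and from .80 to .83.

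**8. Abstinence.** Multiplying the half-width by √(1 − R²): 22.0 × √.98 = 21.8 and 24.4 × √.90 = 23.1 points, a narrowing of 0.2 to 1.3 points over R² of .02 to .10.

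**The case against.** The strongest reply is that the benefit is overstated for this design. Stratifying on cigarettes per day already balances a close relative of the ANCOVA covariate, so part of the apparent gain is a reported standard error that is too large, not a noisier estimate. That stands: the true SD of the estimate falls by about 11%, 6% and 4%, whereas the half-widths in step 3 suggest 19%, 13% and 8% (1 − 3.67/4.55, and so on). It does not remove the power gain. Under stratified randomisation the planned test still has about .73 to .76, against .81 to .89 by ANCOVA, because the oversized standard error is itself what costs rejections.

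Second, every benefit figure depends on a correlation and SD ratio that nobody has stated, and the meaning of SD=8 is open. That also stands. ANCOVA was higher in every scenario tabulated, but at k = 1.25 and rho .7 it is practically level.

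Third, if abstainers have no value for cigarettes per smoking day, the analysed set is selected after randomisation. Baseline balance is then not assured, and the two methods need not estimate the same quantity. This is a real problem, but it affects both methods, and choosing between them does not solve it.

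Finally, this is a Stage 1 pilot, these are additional outcomes, and two of the three items gain little. That limits the importance of the point. It is no reason to leave the adjustment out, given its cost.

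**Conclusion.** The point holds as a recommended improvement. The planned analyses are valid and unbiased, and ignoring the stratum makes them conservative, not liberal.

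The worthwhile gain is for cigarettes per smoking day: power from .74 to about .90, .85 or .80 at rho .3, .5 or .7. This assumes that 8 is the SD of change, SDs are equal at the two visits and all 25 per arm have a value. Depending on the SD ratio the gain may be larger or almost nil, and ANCOVA does not guarantee .80. The .74 is not attributable to the missing stratum term, since that calculation takes no account of stratification.

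For days abstinent the benefit is a correctly sized standard error and 1 to 3 points of power; the estimate itself becomes no more precise. For 7-day abstinence, adjustment is simply unspecified and would change little.

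**What to change.** In both statements of the Aim 2 analysis (Section I, items 4 and 12):

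- Analyse cigarettes per smoking day by ANCOVA: week-8 value on arm and baseline value, with the stratum optional.
- Analyse days abstinent with a linear model containing arm and the randomisation stratum, or with a stratified rank test if the non-parametric route is taken.
- Report the unadjusted results alongside.

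Two related points need their own sentences, because ANCOVA settles neither: how cigarettes per smoking day is handled for participants with no smoking days, and whether SD=8 is the per-visit SD or the SD of change.

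The cost is wording and one or two degrees of freedom, with no new data. If the balanced stratum explains nothing, power for days abstinent is .79 either way. An unrelated continuous covariate would cost about 1 point (.779 against .788, simulated for days abstinent).
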